6.3.6. Week 48 (Visit Window is -7 days)

- Complete physical examination with vital signs (blood pressure, pulse, respiration rate and temperature) and body weight
- Review concomitant medications
- Review adverse events
- Blood sample for serum chemistry and liver function tests (including PT/INR), hematology, plasma HBV DNA level, serum HBsAg (quantitative), HBV serology (qualitative HBsAg and HBeAg), eGFR_{CG}, virology (resistance surveillance), sparse plasma PK (all subjects except Part A, Cohort 2 [ESRD subjects on HD]), vitamin D assessment, and serum and plasma for storage

- Blood sample for Fibrotest®
- CPT ([Appendix 7] Assessment requires: total bilirubin, albumin, PT/INR, Ascites assessment, and Hepatic encephalopathy assessment) for Part B subjects (hepatic impairment) only
- MELD Score (Assessment requires: total bilirubin, serum creatinine, serum sodium, and PT/INR) for Part B subjects (hepatic impairment) only
- Fasting blood sample for serum bone biomarkers and metabolic assessment (glucose and lipid panel [total cholesterol, HDL, direct LDL, and triglycerides]) – no food or drinks, except water, at least 8 hours prior to blood collection
- Fasting urine sample for renal biomarkers for all subjects except Part A, Cohort 2 (ESRD subjects on HD) – no food or drinks, except water, at least 8 hours prior to blood collection
- DXA scan of hip and spine (within –14 days of the expected visit date)
- Health Related Quality of Life (HRQoL) Surveys (CLDQ, SF-36, WPAI, EQ-5D-3L)
- Site-administered questions for Health Utilization Assessment to be completed
- Urine sample (for all subjects except only where available for subjects in Part A, Cohort 2 [ESRD subjects on HD]) for urinalysis, pregnancy test (for females of child-bearing potential; in case of a positive urine test, or if urine cannot be collected for subjects in Part A, Cohort 2 [ESRD subjects on HD], a serum pregnancy test will be done), and for storage.
- ECG (subjects must rest quietly in the supine position for a minimum of 5 minutes prior to the recording)
- Perform study drug accountability
- Dispense study drug
- CCI [REDACTED]

6.3.7. Week 60 (Visit Window ± 14 days)

- Symptom directed physical exam
- Body weight
- Vital signs: blood pressure, pulse, respiration rate, and temperature
- Review concomitant medications

- Review adverse events
- Blood sample for serum chemistry and liver function tests, hematology, plasma HBV DNA level, serum HBsAg (quantitative), HBV serology (qualitative HBsAg and HBeAg), eGFR_{CG}, virology (resistance surveillance), sparse plasma PK (all subjects except Part A, Cohort 2 [ESRD subjects on HD]), and serum and plasma for storage
- Urine sample (for all subjects except only where available for subjects in Part A, Cohort 2 [ESRD subjects on HD]) for urinalysis, pregnancy test (for females of child-bearing potential; in case of a positive urine test, or if urine cannot be collected for subjects in Part A, Cohort 2 [ESRD subjects on HD], a serum pregnancy test will be done), and for storage.
- Site-administered questions for Health Utilization Assessment to be completed
- Perform study drug accountability
- Dispense open label study drugs

6.3.8. Week 72 (Visit Window \pm 14 days)

- Complete physical examination with vital signs (blood pressure, pulse, respiration rate and temperature) and body weight
- Review concomitant medications
- Review adverse events
- Blood sample for serum chemistry and liver function tests, hematology, plasma HBV DNA level, serum HBsAg (quantitative), HBV serology (qualitative HBsAg and HBeAg), eGFR_{CG}, virology (resistance surveillance), sparse plasma PK (all subjects except Part A, Cohort 2 [ESRD subjects on HD]), and serum and plasma for storage
- Fasting blood sample for serum bone biomarkers and metabolic assessment (glucose and lipid panel [total cholesterol, HDL, direct LDL, and triglycerides]) – no food or drinks, except water, at least 8 hours prior to blood collection
- Fasting urine sample for renal biomarkers for all subjects except Part A, Cohort 2 (ESRD subjects on HD)– no food or drinks, except water, at least 8 hours prior to blood collection
- DXA scan of hip and spine (within \pm 14 days of the expected visit date)
- Urine sample (for all subjects except only where available for subjects in Part A, Cohort 2 [ESRD subjects on HD]) for urinalysis, pregnancy test (for females of child-bearing potential; in case of a positive urine test, or if urine cannot be collected for subjects in Part A, Cohort 2 [ESRD subjects on HD], a serum pregnancy test will be done), and for storage.

- Site-administered questions for Health Utilization Assessment to be completed
- Perform study drug accountability
- Dispense study drug

6.3.9. Week 96 (Visit Window is -7 days)

- Complete physical examination with vital signs (blood pressure, pulse, respiration rate and temperature) and body weight
- Review concomitant medications
- Review adverse events
- ECG (subjects must rest quietly in the supine position for a minimum of 5 minutes prior to the recording)
- Blood sample for serum chemistry and liver function tests (including PT/INR), hematology, plasma HBV DNA level, serum HBsAg (quantitative), HBV serology (qualitative HBsAg and HBeAg), eGFR_{CG}, virology (resistance surveillance), sparse plasma PK (all subjects except Part A, Cohort 2 [ESRD subjects on HD]), and serum and plasma for storage
- Blood sample for Fibrotest[®]
- CPT ([[Appendix 7](#)] Assessment requires: total bilirubin, albumin, PT/INR, Ascites assessment, and Hepatic encephalopathy assessment) for Part B subjects (hepatic impairment) only
- MELD Score (Assessment requires: total bilirubin, serum creatinine, serum sodium, and PT/INR) for Part B subjects (hepatic impairment) only
- Fasting blood sample for serum bone biomarkers and metabolic assessment (glucose and lipid panel [total cholesterol, HDL, direct LDL, and triglycerides]) – no food or drinks, except water, at least 8 hours prior to blood collection
- Fasting urine sample for renal biomarkers for all subjects except Part A, Cohort 2 (ESRD subjects on HD) – no food or drinks, except water, at least 8 hours prior to blood collection
- DXA scan of hip and spine (within - 14 days of the expected visit date)
- Health Related Quality of Life (HRQoL) Surveys (CLDQ, SF-36, WPAI, EQ-5D-3L)
- Site-administered questions for Health Utilization Assessment to be completed

- Urine sample (for all subjects except only where available for subjects in Part A, Cohort 2 [ESRD subjects on HD]) for urinalysis, pregnancy test (for females of child-bearing potential; in case of a positive urine test, or if urine cannot be collected for subjects in Part A, Cohort 2 [ESRD subjects on HD], a serum pregnancy test will be done), and for storage.
- Perform study drug accountability
- CCI [REDACTED]

6.4. Post-Treatment Assessments

6.4.1. HBsAg Loss and Seroconversion Subjects

Subjects in Part A (renally impaired) who discontinue study drug due to HBsAg loss with confirmed seroconversion to anti-HBs on or after the Week 24 visit, will be followed off treatment every 4 weeks for 12 weeks and then per the original study visit schedule through Week 96/ED (excluding drug dispensation and accountability). Discontinuation of study drug for subjects experiencing HBsAg loss with confirmed seroconversion, who have known bridging fibrosis or compensated cirrhosis, should be considered on a case by case basis.

Subjects with moderate or severe hepatic impairment (Part B) who experience HBsAg loss and seroconversion to anti-HBs should not discontinue study drug.

6.4.2. All Other Subjects Who Discontinue Study Drug

Subjects in Part A (renally impaired) who have received at least one dose of study drug and permanently discontinue study drug for reasons other than HBsAg loss with confirmed seroconversion to anti-HBs will be followed every 4 weeks for 24 weeks off treatment or up to initiation of appropriate, alternative HBV therapy, whichever occurs first. Use of appropriate, alternative HBV therapy is strongly encouraged.

For subjects in Part B (hepatic impairment) who permanently discontinue study drug, immediate initiation of appropriate, alternative HBV therapy is strongly recommended.

6.4.3. Treatment-Free Follow Up Visit Assessments (Part A Subjects)

- Symptom directed physical exam
- Body weight
- Vital signs: blood pressure, pulse, respiration rate, and temperature
- Review concomitant medications
- Review adverse events

- Blood sample for serum chemistry and liver function tests, hematology, plasma HBV DNA levels, serum HBsAg (quantitative), HBV serology (qualitative HBsAg and HBeAg), eGFR_{CG}, and serum for storage
- Urine for urinalysis

6.5. Early Discontinuation (ED)/Unscheduled Visit

A subject should attend an unscheduled visit if requested by the sponsor or the investigator.

The assessments at the unscheduled visits are at the investigator's discretion. At all unscheduled visits initiated for the purpose of confirming virologic rebound a serum blood sample for resistance testing must be collected.

If a subject discontinues study dosing (for example, as a result of an AE), every attempt should be made to keep the subject in the study and continue to perform the required study-related follow-up and procedures (see Section 6.6, Criteria for Discontinuation of Study Treatment). If this is not possible or acceptable to the subject or investigator, the subject may be withdrawn from the study.

The ED Visit should be performed within 72 hours (i.e., visit window is + 3 days) of the last study drug dose.

- Complete physical exam with vital signs (blood pressure, pulse, respiration rate and temperature) and body weight
- ECG (subjects must rest quietly in the supine position for a minimum of 5 minutes prior to the recording)
- DXA scan of spine and hip to be performed within \pm 14 days of the expected visit date and is done only if not done within the past 12 weeks of the ED visit
- Review concomitant medications
- Review adverse events
- Fasting blood sample for serum bone biomarkers and metabolic assessment (glucose and lipid panel [total cholesterol, HDL, direct LDL, and triglycerides]) – no food or drinks, except water, at least 8 hours prior to blood collection (only collected if not done in the last 12 weeks)
- Fasting urine sample for renal biomarkers for all subjects except for Part A, Cohort 2 (ESRD subjects on HD) – no food or drinks, except water, at least 8 hours prior to blood collection(only collected if not done in the last 12 weeks)

- Blood sample for serum chemistry and liver function tests (including PT/INR), hematology, plasma HBV DNA level, serum HBsAg (quantitative), HBV serology (qualitative HBsAg and HBeAg), eGFR_{CG}, virology (resistance surveillance), sparse plasma PK (all subjects except Part A, Cohort 2 [ESRD subjects on HD]), and serum and plasma for storage
- Blood sample for Fibrotest[®]
- CPT ([Appendix 7] Assessment requires: total bilirubin, albumin, PT/INR, Ascites assessment, and Hepatic encephalopathy assessment) for Part B subjects (hepatic impairment) only
- MELD Score (Assessment requires: total bilirubin, serum creatinine, serum sodium, and PT/INR) for Part B subjects (hepatic impairment) only
- Urine sample (for all subjects except only where available for subjects in Part A, Cohort 2 [ESRD subjects on HD]) for urinalysis, pregnancy test (for females of child-bearing potential; in case of a positive urine test, or if urine cannot be collected for subjects in Part A, Cohort 2 [ESRD subjects on HD], a serum pregnancy test will be done), and for storage.
- Health Related Quality of Life (HRQoL) Surveys (CLDQ, SF-36, WPAI, EQ-5D-3L) are done only if not done within the past 24 weeks of the ED visit
- Site-administered questions for Health Utilization Assessment to be completed

6.6. Criteria for Discontinuation of Study Treatment

Study medication may be discontinued in the following instances:

- Intercurrent illness that would, in the judgment of the investigator, affect assessments of clinical status to a significant degree. Following resolution of intercurrent illness, the subject may resume study dosing at the discretion of the investigator.
- Unacceptable toxicity, as defined in the toxicity management section of the protocol, or toxicity that, in the judgment of the investigator, compromises the ability to continue study-specific procedures or is considered to not be in the subject's best interest
- Therapeutic failure
- Part A (renally impaired) subjects only - HBsAg loss with seroconversion to anti-HBs. These subjects should discontinue study drug within 3-6 months following confirmation of seroconversion to anti-HBs. Subjects with HBsAg loss with confirmed seroconversion before Week 24 are not permitted to discontinue study drug prior to the Week 24 visit.
- Discontinuation of study drug for subject experiencing HBsAg-loss with confirmed seroconversion to anti-HBs, who have known bridging fibrosis or cirrhosis, should be considered on a case by case basis

- Any subject with $eGFR_{CG} < 15$ ml/min who does not initiate hemodialysis or initiates other forms of renal support (e.g. peritoneal dialysis) will be required to discontinue study treatment
- Subject request to discontinue for any reason
- Subject noncompliance
- Pregnancy during the study; refer to [Appendix 5](#)
- Discontinuation of the study at the request of Gilead, a regulatory agency or an institutional review board or independent ethics committee (IRB/IEC)

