Subjects with moderate or severe hepatic impairment (Part B) who experience HBsAg loss and seroconversion to anti-HBs should not discontinue study drug.

Subjects in Part A (renally impaired) who permanently discontinue study drug (either prematurely or after completing 96 weeks of treatment) for reasons other than HBsAg loss with confirmed seroconversion to anti-HBs will be followed every 4 weeks for 24 weeks off treatment or until initiation of appropriate, alternative HBV therapy, whichever occurs first. Use of appropriate, alternative HBV therapy is strongly encouraged.

For subjects in Part B (hepatically impaired) who permanently discontinue study drug, immediate initiation of appropriate, alternative HBV therapy is strongly recommended.

A data monitoring committee (DMC) will review the progress of the study and perform review of safety data after 30 subjects have completed 12 weeks of treatment. However, Gilead will defer to the DMC for any decision to convene earlier or more frequently. The DMC will examine the safety results of the trial and also focus on logistical issues such as accrual, retention, quality of clinical and laboratory data, and implications of results of external studies. No formal stopping rules will be used by the DMC for safety outcomes. Rather, a clinical assessment will be made to determine if the nature, frequency, and severity of adverse effects associated with study treatment warrant the early termination of the study to be in the best interests of the participants.

Number of Subjects
Planned:

Approximately 120 subjects will be enrolled into the 2 Parts of the study:

Part A (renally impaired; approximately 90 subjects):

Approximately 50% (target n = 42 to 46) of subjects enrolled into Part A should be virologically suppressed (HBV DNA < LLOQ) for at least 6 months on TDF or a TDF-containing anti-HBV regimen for CHB at time of Screening.

Approximately 20% (target n = 16 to 18) of subjects enrolled into Part A should have ESRD and be maintained on HD at time of Screening (Cohort 2).

Part B (hepatically impaired; approximately 30 subjects):

Subjects should have moderate or severe hepatic impairment and should be virologically suppressed (HBV DNA < LLOQ) for at least 6 months on TDF, or a TDF-containing anti-HBV regimen, or other OAV(s) for CHB at time of Screening.

Target Population:

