Subjects with decompensated liver disease and active HBV replication are at increased risk of developing progressive liver disease and death {Fattovich 1991}. Furthermore, renal complications occur more commonly in this population, and CHB patients with cirrhosis are also more prone to bone loss and osteoporosis {Chen 2015a}. Peg-IFN is contraindicated in the setting of decompensated liver disease; OAV therapy with either TDF or ETV is recommended {European Association for the Study of the Liver (EASL) 2017, Sarin 2015, Terrault 2015}. With the advent of these potent OAVs for CHB, clinical disease progression can be slowed or reversed {Chang 2010, Marcellin 2013}, and fewer patients with established decompensated liver disease will require liver transplantation while under potent anti-HBV treatment {Zanetto 2016}. While results from Study GS-US-174-0108 suggest that TDF improves the clinical course of patients with decompensated liver disease and is generally safe and well tolerated, confirmed renal abnormalities were observed in a higher percentage of TDF-treated patients compared to those treated with ETV {Liaw 2012}. Results from a recent retrospective analysis in India of 400 CHB patients with cirrhosis, including 210 patients with decompensated liver disease without access to liver transplantation, who were treated with TDF (55%) or ETV (45%) showed higher rates of nephrotoxicity (sCr increase \geq 0.5 mg/dL from baseline) with TDF compared with ETV (5% vs. 1%) when followed for a median of 45 and 36 months, respectively {Goyal 2015}.

Given 90% lower TFV exposures from TAF 25 mg relative to TDF 300 mg once daily, and lack of clinically relevant alteration in the PK of TAF or TFV in moderate or severe hepatic impairment, TAF 25 mg offers the potential for an improved safety profile in CHB patients with hepatic impairment. This study (Part B) will include a cohort of subjects with CPT Class B or C (CPT score 7 to 12 [inclusive]) cirrhosis to assess the safety and efficacy of TAF in this important patient population.

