Subjects in Part A (renally impaired) with HBsAg loss with confirmed seroconversion to anti-HBs should discontinue study drug within 3-6 months following confirmation of seroconversion to anti-HBs. Subjects with HBsAg loss with confirmed seroconversion prior to Week 24 are not permitted to discontinue study drug prior to the Week 24 visit. Subjects with HBsAg loss with confirmed seroconversion will be followed off treatment every 4 weeks for 12 weeks and then per the study visit schedule ([Appendix 2](#)) through Week 96/Early Discontinuation (ED). Discontinuation of study drug for subjects experiencing HBsAg loss with confirmed seroconversion, who have known bridging fibrosis or compensated cirrhosis, should be considered on a case by case basis.

Subjects with moderate or severe hepatic impairment (Part B) who experience HBsAg loss and seroconversion to anti-HBs should not discontinue study drug.

Subjects in Part A (renally impaired) who permanently discontinue study drug (either prematurely or after completing 96 weeks of treatment) for reasons other than HBsAg loss with confirmed seroconversion to anti-HBs will be followed every 4 weeks for 24 weeks off treatment or until initiation of appropriate, alternative HBV therapy, whichever occurs first. Use of appropriate, alternative HBV therapy is strongly encouraged.

For subjects in Part B (hepatic impairment) who permanently discontinue study drug, immediate initiation of appropriate, alternative HBV therapy is strongly recommended.

A data monitoring committee (DMC) will review the progress of the study and perform review of safety data after 30 subjects have completed 12 weeks of treatment. However, Gilead will defer to the DMC for any decision to convene earlier or more frequently. The DMC will examine the safety results of the trial and also focus on logistical issues such as accrual, retention, quality of clinical and laboratory data, and implications of results of external studies. No formal stopping rules will be used by the DMC for safety outcomes. Rather, a clinical assessment will be made to determine if the nature, frequency, and severity of adverse effects associated with study treatment warrant the early termination of the study to be in the best interests of the participants.

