4.3. Exclusion Criteria

Subjects who meet **any** of the following **exclusion criteria** are not eligible to participate in the study:

All Subjects (Parts A & B):

- Pregnant women, women who are breastfeeding or who believe they may wish to become pregnant during the course of the study
- Males and females of reproductive potential who are unwilling to use an “effective”, protocol-specified method(s) of contraception during the study ([Appendix 5](#))

- 3) Co-infection with HCV, HIV, or HDV
 - Subjects who are HCV positive, but have a documented negative HCV RNA, are eligible
- 4) Prior IFN use within 6 months of Screening
- 5) Evidence of hepatocellular carcinoma (i.e. evidenced by imaging within 6 months of Screening)
- 6) Received solid organ or bone marrow transplant
- 7) Significant cardiovascular, pulmonary, or neurological disease in the opinion of the investigator
- 8) Malignancy within 5 years prior to Screening, with the exception of specific cancers that are cured by surgical resection (basal cell skin cancer, etc.). Subjects under evaluation for possible malignancy are not eligible
- 9) Currently receiving therapy with immunomodulators (e.g. corticosteroids), nephrotoxic agents, or agents capable of modifying renal excretion
- 10) Known hypersensitivity to study drugs, metabolites, or formulation excipients
- 11) Current alcohol or substance abuse judged by the investigator to potentially interfere with subject compliance
- 12) Any other clinical condition or prior therapy that, in the opinion of the Investigator, would make the subject unsuitable for the study or unable to comply with dosing requirements.
- 13) Use of investigational agents within 3 months of Screening, unless allowed by the Sponsor
- 14) Use of any prohibited medication as described in Section 5.3.

Part A Only (renal impairment):

- 1) Current or historical evidence of clinical hepatic decompensation (e.g., ascites, encephalopathy or variceal hemorrhage)
- 2) Abnormal hematological and biochemical parameters, including:
 - Hemoglobin < 9 g/dL
 - Absolute neutrophil count < 750/mm³
 - Platelets ≤ 50,000/mm³
 - AST > 10 × ULN

- Albumin < 3.0 g/dL
 - Total bilirubin > 2.5 × ULN
 - INR > 1.5 × ULN (unless stable on anticoagulant regimen)
- 3) Subjects with ESRD (i.e. eGFR < 15 mL/min) not on HD, or those on other forms of renal replacement therapy (i.e. peritoneal dialysis)

Part B Only (hepatic impairment):

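### Section 6.6 allows case-by-case stopping after HBsAg seroconversion in subjects with cirrhosis without naming a Part, and omits the Part B statement made in three other places

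*Protocol*

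**What the plan says.** Section 6.6 of the Protocol lists the circumstances in which study medication may be stopped. Its fourth bullet opens "Part A (renally impaired) subjects only - HBsAg loss with seroconversion to anti-HBs". The fifth is a separate bullet. It begins "Discontinuation of study drug for subject experiencing HBsAg-loss with confirmed seroconversion to anti-HBs" and continues "who have known bridging fibrosis or cirrhosis, should be considered on a case by case basis".

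Section 3.1 has a parallel sentence inside its Part A paragraph, with a narrower population: "who have known bridging fibrosis or compensated cirrhosis, should be considered on a case by case basis". The Synopsis and Section 6.4.1 use the same narrower wording in the same position. Each of the three places then makes a separate statement about Part B. Section 6.4.1 puts it as: "Subjects with moderate or severe hepatic impairment (Part B) who experience HBsAg loss and seroconversion to anti-HBs should not discontinue study drug". The Synopsis likewise says of Part B subjects "who experience HBsAg loss and seroconversion to anti-HBs should not discontinue study drug". Section 6.6 has no such statement.

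**The concern.** Section 6.6 is the list that Section 6.5 points to when a subject stops dosing, so sites are likely to consult it on its own. Read alone, it can suggest that stopping is open to individual judgement for a Part B subject with cirrhosis, whereas three other places say that such a subject stays on drug.

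The matter at stake is antiviral treatment in people with advanced liver disease, for whom Section 1.4 describes therapy as lifelong. The scheduled off-treatment visits in Sections 6.4.1 to 6.4.3 are also written for Part A. A Part B subject stopped under the Section 6.6 bullet would have no defined off-treatment visit schedule beyond the general request in Section 6.5 to keep the subject in follow-up.

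**Working it through.** The point rests on comparing texts. The plan gives no figure to reproduce.

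**Step 1. The places side by side.**

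| Place in Protocol | Case-by-case sentence sits in | Cirrhosis wording | Says Part B is not to stop? |
|---|---|---|---|
| Synopsis, Study Design | Part A paragraph | compensated only | Yes |
| Section 3.1 | Part A paragraph | compensated only | Yes |
| Section 6.4.1 | Part A paragraph | compensated only | Yes |
| Section 6.6 | its own bullet, no Part named | unqualified | No |
| Appendix 2, footnote m | absent | – | No |

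Three places agree with each other. Section 6.6 differs from them in three respects: the Part label, the word *compensated*, and the Part B statement.

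**Step 2. Does the Section 6.6 wording reach Part B?** Section 1.3 says: "This study (Part B) will include a cohort of subjects with CPT Class B or C (CPT score 7 to 12 [inclusive]) cirrhosis". Unqualified cirrhosis therefore includes these subjects. Part A, by contrast, excludes "Current or historical evidence of clinical hepatic decompensation (e.g., ascites, encephalopathy or variceal hemorrhage" (Section 4.3), so dropping *compensated* changes little within Part A. The difference matters mainly if the bullet extends to Part B.

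Part B is also not uniformly decompensated. Section 4.2 admits subjects with a past CPT score of at least 7 and any score up to 12 at Screening, so some may be in Class A (score 5–6, Appendix 7) at entry. The Part B statement refers to moderate or severe hepatic impairment and does not say outright whether it includes them. The Section 6.6 bullet would cover them if they have known cirrhosis.

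**Step 3. Does anything printed confine the bullet to Part A?** Only its position after the bullet labelled for Part A. Other unlabelled bullets in the list, such as those on toxicity, noncompliance and pregnancy, apply to every subject, so a missing label does not by itself signal Part A.

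**Step 4. How often could it arise?** The only counts in the Protocol are the Week 48 results in Section 1.2.3, with group sizes from Table 1-1.
- HBeAg-positive study, TAF: 4 of 581 lost HBsAg, and 3 of these 4 seroconverted. 3/581 = 0.52%.
- HBeAg-negative study, TAF: 0 of 285 lost HBsAg.
- Together: 581 + 285 = 866, and 3/866 = 0.35%.

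Median HBV DNA at entry to these studies was 7.9 and 5.7 log10 IU/mL respectively. Part B subjects must be below 20 IU/mL at Screening after at least 48 weeks of treatment. The counts show that the event is rare. They do not give a rate for Part B.

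**The case against.** The strongest reply is that Section 6.6 already limits this criterion to Part A. The only bullet that names HBsAg loss as a reason to stop carries the Part A label. The next bullet does not complete the list's opening line; it reads as a qualification of the bullet above, just as the parallel sentence closes the Part A paragraph in the other three places. It may even be a sub-bullet whose indentation was lost when the PDF was read. The Part B statement appears three times, once in the section devoted to seroconverters.

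Much of this stands. The Part A reading is plausible and may well be what was intended, so a reader who infers that the Protocol deliberately permits stopping in Part B goes too far. The reply does not settle the matter, because nothing in the printed text ties the bullet to the one above. Even on the Part A reading, the cirrhosis wording differs from the other places and the Part B statement is missing from the list.

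A reader might also infer that the Protocol would leave such a subject untreated and exposed to decompensation. It does not say so. Section 6.4.2 strongly recommends immediate alternative HBV therapy for any Part B subject who permanently stops. The warning in Section 7.5.5.1 concerns ALT flares and discontinuation with treatment-free follow-up.

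**Conclusion.** The inconsistency is real and should be corrected. It is one of wording: as printed, Section 6.6 can be read to cover Part B and so to conflict with the Synopsis and Sections 3.1 and 6.4.1. The conclusion assumes only that a site may read the list as it stands. Its practical reach is small, because the bullet applies only after confirmed seroconversion.

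Three further inferences are tempting but unsupported:

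- **That such a subject drops out of the Week 48 and 96 results.** The Full Analysis Set keeps everyone enrolled who took at least one dose (Section 8.2.1.1), missing categorical efficacy outcomes count as failures (Section 8.3), and Section 6.5 asks sites to keep the subject in the study. What is cut short is the safety summary, which runs to the end of treatment (Section 8.6).
- **That the Phase 3 frequency gives a probability for Part B.** All three events came from the HBeAg-positive study, in viremic subjects followed to Week 48. Applying that rate to suppressed subjects with hepatic impairment over 96 weeks has no basis in the documents, and a chance of seroconversion would not be a chance of harm.
- **That all of the approximately 30 Part B subjects are affected.** Only one who seroconverts would meet the conflicting texts.

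**What to change.** Reconcile Section 6.6 with the Synopsis and Sections 3.1 and 6.4.1:

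1. Have the bullet name the Part to which it applies.
2. Use the same cirrhosis wording in all four places.
3. Put the Part B statement in Section 6.6, in whatever form the sponsor confirms. It would help to say whether it includes Part B subjects who enter on a past CPT score.

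The clinical rule is for the sponsor to decide; the request is only that the four places then agree. The cost is a line or two in an amendment, or a clarification letter to sites. No analysis changes.
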